1.0 Purpose

The primary purpose of this prospective, randomized, multicenter study is to evaluate and compare the amount and quality of tissue samples yielded in a liver biopsy comparing 2 different techniques of EUS guided CORE liver biopsy for benign disease. The two techniques: “Modified Wet suction” and “Slow pull” technique of collecting tissue from a liver biopsy via Endoscopic Ultrasound (EUS).

2.0 Background

Endoscopic Ultrasound (EUS) for tissue acquisition has undergone significant advances over the past 10 years. EUS guided fine needle biopsy (FNB) and CORE biopsy techniques have rapidly come to the forefront. With the advent of changes to needle design and the study of techniques for tissue acquisition, FNB and Core biopsies will allow for a revolution in tissue acquisition.

The safety and efficacy of EUS guided liver biopsy for acquisition of histologic samples (FNB, “biopsy” or “core”) has been demonstrated in initial studies ¹⁻⁷. These initial studies demonstrated the ability to safely obtain adequate liver specimens based on size of specimen and number of portal tracts ¹⁻⁷. Diehl et al also noted that EUS guided liver biopsy offers significant advantages including increased patient satisfaction, ability to avoid a second procedure for biopsy, and EUS guidance can be used to avoid large vessels and perform diagnostic evaluation of adjacent structures³. In addition to patient satisfaction, a reduction in cost may be seen as well in the appropriate settings where a patient already requires EUS for evaluation of dilated biliary system or other indications – as opposed to having the liver biopsy done as a separate additional procedure. While there has been a high level of adequacy, diagnostic yields have varied from 86-100% ^{1,3,5,6} indicating the technique must be refined and studied further.

The efficacy and safety of EUS guided biopsy is dependent on technique, needle and specimen processing, which provides opportunity for improvement of clinical outcomes.

The use of suction has not offered a clear benefit in the quality of specimen. The cellularity, yield and bloodiness of the specimens, account for the lack of clarity. The use of a wet suction technique has been introduced to provide a larger tissue volume and decrease bloodiness ^{8,9}. Endoscopic Ultrasound (EUS) with Fine Needle Aspiration (FNA) has traditionally been performed using a dry suction technique. As opposed to the wet suction technique, which is performed using a needle flushed with saline, the dry suction technique utilizes an empty needle, essentially filled with air. The proposed advantage of the wet suction technique and the basis for the study relies on the fundamentals of fluid mechanics, as saline water is substantially less compressible than air. This difference in compressibility allows a greater “pulling force” to be generated from drawing back the plunger upon aspiration and in turn, more tissue is suctioned for biopsy.

Software simulation demonstrated the wet suction technique to allow faster aspiration and to aspirate 70% more tissue for a simulation time of 0.1 seconds, as compared to the dry technique ⁴.

Recently two companies have released novel designs to obtain histologic specimens for core biopsy. The technique for obtaining optimal tissue samples has not been well defined, but there has been tendency towards slow pull or “wicking” to obtain larger histology ¹².

We aim to further refine EUS guided liver biopsy with use of novel needle technology in conjunction with Fine needle biopsy – “FNB” – for Core histology acquisition by comparing two widely accepted techniques in a randomized, multi-center prospective trial.

3.0 Study Objectives

3.1 Objective

- a. To determine if there is a significant difference in pathological yield as determined by fragmentation, length and number of portal tracts of the biopsy sample between a “modified wet suction,” and a “slow pull” techniques in obtaining CORE of histologic tissue from nonmalignant liver per EUS.

3.2 Secondary Objective

- a. To identify complications within one week that are associated with each technique.
- b. To identify the time required for each step of the individual procedures.
- c. To identify additional findings of the procedure not related to liver disease
- d. To identify any diagnostic differences in pathological findings between left and right liver lobe specimens

4.0 Study Design

This is a randomized prospective multicenter trial. At least 160 subjects will be enrolled. Enrollment is projected to be completed within approximately 12 months. Subjects will undergo a liver biopsy consisting of two passes using one of 2 methods: “modified wet suction” (**Arm 1**) and “slow pull” (**Arm 2**).

Up to twenty (20) participating U.S. sites will consist of tertiary referral centers (either academic or community). The participating physicians are required to have experience as advanced interventional expert endoscopists as demonstrated by prior experience of performing a minimum of twenty EUS guided liver biopsies, and performing greater than 350 EUS procedures per year.

Adult (> 18 years old) subjects who will undergo EUS guided liver biopsy may be included in this study. EUS liver biopsy will be performed if clinically indicated as part of standard of care for clinical workup. This includes patients who need an Esophagogastroduodenoscopy

(EGD) and have any indication for liver biopsy. The initial indication for EUS may not be solely for EUS liver biopsy but rather may be for other indications as well (such as chronic pancreatitis, ductal dilation, right upper quadrant abdominal pain, etc.).

The study duration will commence at the time of Informed Consent for the EUS guided liver biopsy procedure and conclude one-week post procedure.

Subjects will undergo a liver biopsy consisting of two passes using one of 2 methods: “modified wet suction” (**Arm 1**) or “slow pull” (**Arm 2**). A randomization process will determine which Arm will be utilized. Each subject shall undergo two passes (two cores of tissue will be obtained – ideally from the right and left lobe of the liver. However, if this is not technically possible – per discretion of the endoscopists – it will be noted and two biopsies will be obtained from the same lobe of the liver.). Standard hospital protocol will be followed for patient care management following procedure.

Quality of tissue obtained via the two different techniques will be evaluated by number of fragments, length of specimens and number of tracts observed by the local pathologist and compared between the tissues obtained from the two techniques. We will also note technical success rate (ability to insert the needle twice into the liver for obtaining two specimens, incidence of a dry pass and ability to pass into the right and left lobe of the liver).

Complications will be observed and reported up to one-week post procedure. (Complications may include additional visit to clinic or ER visit, bleeding requiring medical attention, infection requiring interventions, liver laceration, admission post procedure, or need for surgery).

The EUS guided biopsy will follow the procedural description in Section 8.

Follow up evaluations and treatment will be performed in accordance with standard of care procedures and procedures deemed necessary by the attending physician.

The participating site will obtain appropriate Institutional Review Board (IRB) approval prior to participating in any research activities. A Central IRB review will be conducted for those sites that are able to accept a Central IRB determination. For other sites that require local IRB approval, the participating site will provide PRC with a copy of their IRB approval prior to any study procedures. PRC will also need to collect the local IRB’s IRB registration and/or FWA to confirm compliance.

Once IRB approval has been confirmed by the coordinating site and the Site Initiation Visit (SIV) is completed, the participating site will receive enrollment instructions, randomization envelopes and case report forms.

All processing of specimens will be performed according to The College of American Pathologists. The designated pathologist(s) at each site will be responsible for reading all study specimens as described in Appendix A.

5.0 Selection of Patients

Candidates for this study are patients who will be undergoing liver biopsy under EUS guidance and are deemed to have clinical need for liver biopsy for non-malignant processes.

All patients determined by the physician to be clinically in need of a liver biopsy via EUS may be approached for possible enrollment. Usually these are patients requiring an upper endoscopy and a liver biopsy as part of workup for liver disease.

6.0 Eligibility

6.1 Inclusion Criteria

- 6.1.1 Subjects that plan to undergo a liver biopsy via EUS to confirm possible underlying liver disease or to determine stage, grade and presence of fibrosis for suspected benign etiology.
- 6.1.2 Subjects with a history of abnormal LFTs (as designated by attending gastroenterologist), documented history of chronic liver disease, history of fatty liver disease or have a question of underlying liver disease as cause of abnormal imaging, labs or symptoms which may be attributed to liver disorder and may benefit from liver biopsy or other clinical indication for liver biopsy
- 6.1.3 Subjects 18 years of age or older
- 6.1.4 Subject must be able to hold anticoagulants as per institutional standard of care
- 6.1.5 Subjects must be deemed physically able to undergo anesthesia. This includes either Monitored Anesthesia Care (MAC) or general anesthesia.
- 6.1.6 Subjects that have agreed to participate in the study and have signed Informed Consent
- 6.1.7 Women of child bearing potential who are not pregnant as proven by a negative pregnancy test.

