8.8 Randomization

Subjects will undergo a liver biopsy consisting of two passes using one of 2 methods: "modified wet suction" (Arm 1) and "slow pull" (Arm 2). Subjects in each of the two specimen processing groups will be randomized into each arm in a balanced manner to either the "modified wet suction" technique (ARM 1), or the "slow pull" technique (ARM2) when performing liver biopsy according to a predetermined randomization. Randomization will be stratified by site, with a block size of 4.

A numbered, sealed envelope will be utilized to identify randomization of each subject; these will be provided by study sponsor. A sheet of paper inside the envelope will indicate either ARM 1 –

Modified Wet Suction technique or ARM 2– Slow Pull technique. The envelope may be opened after the Informed Consent and Eligibility Checklists are completed. Often the Randomization envelope will be opened once the patient is in the procedure room.

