8.12 Total EUS time

Beginning of EUS examination which begins when the EUS scope is placed into the patient's mouth to when the EUS scope is withdrawn. EGD time prior to EUS is not counted. Room set up and anesthesia time is variable and not counted.

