8.17 Adverse Event Evaluation

Adverse events will be collected starting after randomization occurs and for one (1) week post-Biopsy. No additional visits are required for the study. Record review may suffice for obtaining follow-up information, See Section 9, Adverse Event Reporting, for more information.

8.18 Recovery:

From time out of room until patient is ready to be released. This time will be noted by recovery room personnel. The patient does not need to actually leave; but ready for discharge.

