12.3 Statistical Analysis

The two techniques will be compared for differences in fragmentation, total specimen length, and number portal tracts of the tissue using generalized linear mixed effects models (GLMM). The GLMMs will compare the two techniques while incorporating random effects for study site and endoscopist using the appropriate distribution and link function for each outcome (e.g. negative binomial distribution with log link for count data, binomial distribution with logit link for binary data). The GLMMs will also include a random effect to allow correlation between the two biopsy samples from each subject and a fixed effect to allow comparison between the two sides; an interaction between side and technique will be examined but removed from the model if not significant. Similar GLMM analyses will be performed for the comparisons of complications, technical success rate, total EUS time, total liver biopsy time, and recovery time. Analyses will be performed with sample processing technique included as a covariate in the analyses. Because of the small number of subjects with the mesh prep technique, the interaction between study group and sample processing technique will not be examined. Additionally, the analyses will be repeated after removing the subjects with the mesh prep technique. A 5% significance level will be used for all tests.

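### Recovery time is compared between techniques with no term for anesthesia type, and the type is not listed as collected; the likely cost is some precision on a non-primary outcome.

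*Combined protocol and SAP*

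**What the plan says.** Criterion 6.1.5 admits subjects fit for anesthesia of either kind: "This includes either Monitored Anesthesia Care (MAC) or general anesthesia". No section gives the expected mix or ties a site to one type.

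Section 8.18 defines recovery: "From time out of room until patient is ready to be released". Section 12.3 then says: "Similar GLMM analyses will be performed for the comparisons of complications, technical success rate, total EUS time, total liver biopsy time, and recovery time". The model it refers back to is described as "incorporating random effects for study site and endoscopist", with further terms for subject and for liver side. One covariate is named: "Analyses will be performed with sample processing technique included as a covariate in the analyses". Anesthesia type is not mentioned.

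The only remark on anesthesia as a source of variation is in 8.12, on the EUS clock: "Room set up and anesthesia time is variable and not counted".

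On allocation, 8.8 states: "Randomization will be stratified by site, with a block size of 4". On timing it adds: "Often the Randomization envelope will be opened once the patient is in the procedure room". Section 8.9 describes randomization as taking place after the upper endoscopy and the diagnostic EUS.

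**The concern.** Recovery time as defined covers the period in which the patient comes round from anesthesia, so it is the procedure time most exposed to the kind of anesthesia given. The protocol keeps anesthesia time out of the EUS clock but makes no comparable provision for recovery.

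If one site uses both types and they lead to different recovery times, an unadjusted comparison carries that difference as extra residual variance. The confidence interval for the technique effect is then wider than it need be. If the type is not recorded prospectively, later adjustment depends on going back to the charts.

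What is at stake is the precision of one comparison outside the primary endpoint. Section 12.2 does not name recovery time; it refers only to the time needed for procedural steps. Section 11.0 powers the study on length and number of tracts.

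**Working it through.** **The plan's own figure.** Section 11.0 gives 72 completers per group for 80% power, a 20% difference in means, CV 0.4 and a two-sided 5% test of a ratio.
- SD on the log scale = sqrt(ln(1 + 0.4²)) = 0.3853; difference = ln(1.2) = 0.1823.
- Normal approximation: n = 2 × (1.960 + 0.842)² × 0.3853² / 0.1823², which rounds up to 71. The noncentral t gives 72, with 80.5% power.
- With 10% loss, 72 / 0.9 = 80 per group.

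The figure reproduces and does not depend on this point. No figure is stated for recovery time.

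**Is the type collected?** It does not appear in the schedule of events (7.0), the timing sections (8.12, 8.13, 8.18), the post-biopsy summary (8.16) or the patient-file list (14.5). Concomitant medications (8.6) might capture the agents used, but do not define the type.

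**Size of the precision loss.** The documents give no mix, no recovery-time SD and no effect of type, so these are assumptions: a share p under general anesthesia of 0.10 to 0.50, and a gap g between types of 0.25 to 1.0 residual SD. First take all the variation to lie within site and endoscopist. The omitted term adds variance p(1−p)g² in residual units, so

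SE ratio (unadjusted / adjusted) = sqrt(1 + p(1−p)g²).

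| p | g = 0.25 | g = 0.5 | g = 1.0 |
|---|---|---|---|
| 0.10 | 1.003 | 1.011 | 1.044 |
| 0.25 | 1.006 | 1.023 | 1.090 |
| 0.50 | 1.008 | 1.031 | 1.118 |

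Anesthesia type then accounts for 0.6% (0.005625 / 1.005625) to 20% (0.25 / 1.25) of the variance. The formula is for a linear model, so for a GLMM it is an approximation on the scale where the model is linear.

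**In power terms, for illustration only.** Borrow the CV of 0.4 and ratio of 1.2 from section 11.0 as if they described adjusted recovery time, with 80.5% power at 72 per group. Unadjusted power then runs from 80.3% down to 71.3%. If site effects absorb half of the added variance, it runs from 80.4% to 75.8%. If a site uses one type only, there is nothing to gain there.

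**Type I error.** A simulation used 144 subjects in 36 blocks of 4, 30% under general anesthesia independently of arm, a gap of 1 SD and no technique effect. The unadjusted t test rejected in 4.9% of 20,000 runs.

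**Chance imbalance.** Take p = 0.2, g = 1 and 72 per group. The between-arm difference in the share has SD sqrt(2 × 0.16 / 72) = 0.067. The adjusted SE is sqrt(2 / 72) = 0.167 and the unadjusted SE is sqrt(2 × 1.16 / 72) = 0.180. Since 0.167² + 0.067² = 0.180² after rounding, the imbalance is already inside the unadjusted SE and is not a second effect.

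**The case against.** The strongest reply is that leaving a prognostic covariate out of a randomized comparison is not an error, and that this one rests on clinical expectation. No section says recovery differs by type. The remark in 8.12 explains what falls outside the EUS clock and says nothing of recovery. Age, or dilation during the upper endoscopy, could be argued for in the same way. That stands: this is an improvement, not a correction, and its size is assumed throughout.

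Second, site and endoscopist are random effects and randomization is stratified by site, so variation that follows local practice is largely dealt with. This also stands. A reader might infer that the whole difference between types remains in the error; 12.3 does not support that.

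Third, a reader might infer that anesthesia type is always settled before the arm is known, making it a baseline covariate by design. Section 8.9 describes that order, but 8.8 allows the envelope to be opened as soon as consent and the eligibility checklist are complete, and says only that it is often opened in the procedure room. The order is the described workflow, not a requirement. This does not defeat the proposal, but it means timing must be recorded and the unadjusted result kept in view.

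Finally, the case report forms are separate and not shown, so they may already hold the type. If so, only the covariate is needed.

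**Conclusion.** The point holds as a low-cost refinement. Both types are allowed, recovery time is tested at 5%, the model has no anesthesia term, and the protocol does not list the type as a data item. The expected cost is a standard error about 0.3-12% larger than necessary, on assumed shares of 10-50% and gaps of 0.25-1.0 SD with all variation within site and endoscopist. It is smaller where practice follows site or operator, and nil at sites using a single type.

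A reader might go further and infer that the unadjusted comparison is biased or its test invalid. The documents do not support that: allocation is random within site, and the simulated rejection rate was 4.9%. That reasoning assumes the choice of anesthesia does not depend on the arm, which the workflow in 8.9 makes likely but 8.8 does not guarantee.

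**What to change.** Record on the procedure CRF the anesthesia type as started for the EGD/EUS, and whether it was started before the randomization envelope was opened. For subjects already treated, take both from the anesthesia record where it allows.

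In 12.3, prespecify anesthesia type as a fixed covariate in the recovery-time model only, and report the unadjusted result alongside it. The second result matters because an envelope opened before anesthesia could let the arm influence the type, and adjustment would then condition on something that happened after allocation.

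The cost is one CRF field with a timing check, some chart retrieval, and one extra model parameter. Anesthesia practice does not change.

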6.2 Exclusion Criteria

- 6.2.1 Subjects that are undergoing the EUS procedure for malignant process.
- 6.2.2 Subjects unable to tolerate anesthesia for the procedure
- 6.2.3 Subjects who cannot undergo or refuse EUS guided procedure
- 6.2.4 INR >1.5 (if tested per individual institutional protocol)
- 6.2.5 Subjects that have taken aspirin in the 5-7 days prior to procedure (or as required by individual institutional protocol)
- 6.2.6 Platelets 50,000 uL or less

- 6.2.7 Subjects with evidence of significant upper gastrointestinal bleeding prior to endoscopy
- 6.2.8 Subjects requiring endoscopic mucosal resection
- 6.2.9 Subjects with large volume ascites as determined by subject's clinician
- 6.2.10 Subjects requiring pancreatic biopsies
- 6.2.11 Subjects that have not held antiplatelet or other anticoagulant medications for adequate time prior to procedure as per institutional policy

7.0 Schedule of Events

	Screening +/- 7 days	Biopsy Day of Procedure	1 Week post-Biopsy
Informed Consent	X		
Eligibility Checklist	X		
Demographics	X		
Medical History	X		
Concomitant Medications	X		
Laboratory Assessments *	X		
Randomization		X	
EUS Guided Liver Biopsy		X	
Pathology Assessment		X	
Adverse Event Evaluation		X	X
Post Biopsy Clinical Summary			X

** Laboratory assessments **may** include Albumin, Alkaline Phosphatase, ALT/SGPT, AST/SGOT, Total Bilirubin, Direct Bilirubin, Indirect Bilirubin, Lipase, Total Protein, platelets, INR, serum pregnancy if applicable, Fibroscan, Fibrosure and Hepatitis Panel results (these laboratory assessments will be performed per institution Standard of Care)*

8.0 Conduct of Study Assessments and Study Procedures

8.1 Informed Consent

Informed consent must be obtained before performing any study-specific procedures. Subjects will receive a consent form to read in person. They will be instructed to read the consent and write down any questions they may have. They will be allowed as much time as they need to read the consent form.

It will be stressed to the subjects that this is voluntary and in no way will it impact their medical care. Study Staff will then review the consent document with the subject to ensure that they understand the study.

The subject must have all questions pertaining to the study answered satisfactorily. The consent form that is used must be approved by both the reviewing IRB and by PRC. One copy of the

completed informed consent form must be given to the subject and the original must be placed in the subject's medical record as a source document.

8.2 Eligibility Checklist

Prior to any study procedures, the eligibility checklist will be completed and signed.

8.3 Subject ID # Assigned

Upon enrollment into the clinical study, a unique subject study ID will be assigned. The subject number will be assigned consecutively in ascending order per site. The subject study ID number should be recorded on all source documents.

